randomization procedure.⁸⁸ **Covariates (to adjust for potential confounding) and potential moderators will include the following:** mode of delivery of SMA (in-person vs. telehealth), age, gender, race/ethnicity, comorbidity index, insulin dependence, baseline diabetes distress, health literacy, and mental illness. Recent literature on cluster randomized trials notes that imbalance in covariates is more of a problem than for individually randomized trials, and covariates should be included to improve precision and should be selected prior to analysis.^{55,88,89} In the event normality assumptions are not met, we will use transformations to normalize distributions, ordinal or Poisson regression where appropriate, and/or the appropriate link function (e.g. logit link for dichotomized measures).⁹⁰⁻⁹² We will employ intent to treat analyses using general (generalized) linear mixed models (GLMMs) to incorporate data structures that are both hierarchical and longitudinal.^{91,93-97} Hypothesis tests will be two-sided with $\alpha = .05$ or p values reported. Goodness of fit statistics and model fitting diagnostics will be used to assess for influential points, outliers, overdispersion and heteroscedasticity and to evaluate alternative model specifications.⁹⁰ All statistical analyses will be performed using SAS version 9.4 (SAS Institute Inc., Cary, N.C.).

Missing Data (MD-2). Prior to beginning analyses described below to address study hypotheses, we will examine the data carefully to determine whether patterns of missing are ignorable (MCAR or MAR) or non-ignorable (MNAR).⁹⁸⁻¹⁰¹ If so, we will employ likelihood-based methods that utilize all available data (MD-4), adjusting for covariates that are associated with missingness (MD-3). If missingness is non-ignorable we will employ pattern mixture models.¹⁰² Sensitivity analyses will be carried out using multiple imputation approaches (MD-5).

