In the model above we use practice level random effects. However, it is possible that groups (within practices) are a greater source of variation than practices per se. Therefore, we will estimate variance components for groups within practices and retain both random effects if there is sufficient variability. If it is not possible to retain both group and practice random effects, we will test each separately and examine model fit and variance components to determine which to retain.

To test hypothesis II (comparing clinical outcomes): Outcomes for these analyses will be obtained from EHR data covering 9 months' post-baseline for each patient. The baseline measure for each clinical outcome will be defined as the last recorded value prior to enrollment in the study. All subsequent clinical measures through 9 months after enrollment will be used in analysis. Analytic approaches will be similar to those described for hypothesis 1, with time will be coded

PRINCIPAL INVESTIGATOR (LAST, FIRST, MIDDLE): [name]

as time since baseline. Random coefficient growth curve models will be used to determine whether trajectories for patients in standard SMA practices differ from patients in patient-driven SMA practices (time x arm interaction term in mixed model notation).

Hypothesis III. Compared to standardized diabetes SMAs, practices using patient-driven diabetes SMAs will exhibit greater improvements in quality and team-based care, as measured by the Relational Coordination Survey and the Assessment of Chronic Illness Care.

To test ***hypothesis III (comparing patient reach and engagement)***. The outcomes for these analyses will be 1) acceptance of services (Y/N), and 2) number of SMA sessions attended. General or generalized linear mixed effects models (depending on distribution of outcomes variable) with a practice random effect will be used for analysis. In addition to including covariates as described above, we will test whether mental illness is a moderator of intervention effectiveness. This will involve including a main effect for mental illness, along with an arm x mental illness interaction term (mixed model notation).

To test ***hypothesis IV (comparing practice quality and team based care)***: Outcomes for this analysis will be scores on the relational coordination survey and the ACIC at baseline, 9, and 24 months. Analytic approaches will be similar to those described for hypotheses I and II.

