Heterogeneity of treatment effects (HTE) (HT-2). It is not known at this time whether patient-driven SMAs will benefit certain patients more than others. Thus, in addition to the analyses described above, we will conduct exploratory analyses to test for potential effect modification (moderator of intervention effectiveness) by selected patient characteristics (HT-1). While this study may be powered to detect effect modification with large effect sizes, the planned sample size of 1000 enrolled will allow only for testing effect modification of patient characteristics representing subgroups of an average of 10 patients per practice with that characteristic. For example, to do a subgroup analysis of patients with mental illness, we would need an average of 10 patients with mental illness per practice to test this effect. This analysis is described just above for analysis of hypothesis IV with mental illness as a potential moderator; mental illness comorbidity is our primary target for HTE analyses and will be examined for every hypothesis above. Additional sub-populations of interest are defined by gender, Hispanic ethnicity, and health literacy; existing evidence suggests possible differential participation and effectiveness for these groups.^{29,108,109} The general hypothesis for these moderator analyses is as follows: The effects of the patient-driven vs standardized SMAs on diabetes distress (and other primary and secondary outcomes) will differ for patients with mental illness compared to patients without mental illness (male vs. female, Hispanic ethnicity vs not, high vs. low health literacy, food security, cohort conducted in English or Spanish, virtual vs. in-person, insulin dependence). To assess for possible heterogeneity of treatment effects by mode of delivery (effect modification, moderator) additional analyses will be performed including the appropriate two and three-way interactions between treatment arm and mode: arm x modality interaction for single outcomes, arm x time x modality along with relevant two-way interactions for longitudinal analyses. Additionally, sensitivity analyses will be performed to further explore delivery mode. Additionally, we will examine variability between SMA groups separately for standard and patient-driven arms to determine if the group itself (especially in the patient-driven arm) is an important contributor to differences in outcomes.

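### The exploratory arm-by-delivery-mode test on sessions attended has no SMA cohort term, so it rejects too often where mode varies between cohorts within a practice and attendance is correlated within cohorts

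*Combined protocol and SAP*

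**What the plan says.** All references are to the combined protocol and SAP, mainly section C4.4.2d.1.

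- **Hypothesis III outcomes.** "The outcomes for these analyses will be 1) acceptance of services (Y/N), and 2) number of SMA sessions attended". Each gives one value per patient.
- **Hypothesis III model.** "General or generalized linear mixed effects models (depending on distribution of outcomes variable) with a practice random effect will be used for analysis". Nothing below practice is named.
- **Group effect.** This provision comes directly after the hypothesis I equation and begins "In the model above we use practice level random effects". It concedes that "it is possible that groups (within practices) are a greater source of variation than practices per se" and continues: "we will estimate variance components for groups within practices and retain both random effects if there is sufficient variability". Hypotheses II and IV are said to follow a similar approach. Hypothesis III is given its own model, without this provision.
- **Moderators.** The paragraph on heterogeneity of treatment effects introduces the moderators as patient characteristics, but its list includes "food security, cohort conducted in English or Spanish, virtual vs. in-person, insulin dependence". For delivery mode it plans an "arm x modality interaction for single outcomes". It also says that variability between SMA groups will be examined separately by arm.
- **Level of the moderators.** The note on mode of delivery (section C.4.3.1c) has practices document the delivery option of their groups. It also reports that in-person visits stopped in March 2020 and resumed at different rates. Language is defined on the cohort.
- **Status.** Moderator analyses are exploratory and not adjusted for multiplicity. All will be reported, and their number will be taken into account in interpretation.

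**The concern.** Delivery mode belongs to a whole cohort of 8 to 10 patients. If a practice runs some cohorts in person and others by telehealth, the evidence for an arm-by-mode interaction comes from comparing cohorts within practices. A practice intercept removes differences between practices. It does not carry differences between cohorts of the same practice.

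Attendance may well be similar within a cohort, whose members share a meeting time, instructors and group dynamics. The practice-only model treats such patients as independent given the practice. Its standard error for the interaction is then too small.

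At stake is a false signal that mode changes which SMA model engages patients better. The dissemination section wants the results to help practices decide which model suits them and for which patients, so such a signal could be acted on.

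**Working it through.** **Inputs from the documents**
- Two-sided alpha of 0.05 ("Hypothesis tests will be two-sided with $\alpha = .05$ or p values reported").
- 22 practices, 11 per arm, and 1,000 patients (C.4.1, sample size paragraph), so 1,000/22 = 45.5 per practice, as section D also states.
- Cohorts of 8 to 10 (C.4.1). Taking 9, 45.5/9 is about 5 cohorts per practice. C.4.1 also mentions around 8 cohorts, which was run as an alternative.
- Practice-level ICC of 3% and 5% (power table).

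**Assumed, because the documents do not give them:** the cohort ICC for attendance, and the mix of modes within practices.

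**1. The plan's own figures.** Effective sample size = n / (1 + (m − 1) × ICC).
- ICC 3%: 445 / (1 + 43.5 × 0.03) = 445 / 2.305 = 193.1 (stated: 193).
- ICC 5%: 445 / (1 + 43.5 × 0.05) = 445 / 3.175 = 140.2 (stated: 140).

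The other four rows reproduce as well (181.2, 133.9, 76.3, 67.1). The table allows for clustering by practice. It gives no figure for an arm-by-mode test.

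**2. Closed form for a cohort-level contrast judged against patient-level error.** Design effect DE = 1 + (m − 1) × ρ, where ρ is the cohort ICC. Actual type I error = 2 × (1 − Φ(1.96/√DE)). With m = 9:
- ρ = 0: DE = 1, type I error 5.0%.
- ρ = 0.03: DE = 1.24, 1.96/1.114 = 1.76, type I error 7.8%.
- ρ = 0.05: DE = 1.40, 1.96/1.183 = 1.66, type I error 9.8%.
- ρ = 0.10: DE = 1.80, type I error 14.4%.

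At ρ = 0.05 the result is 9.2% for m = 8 and 10.4% for m = 10.

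**3. Simulation with no true interaction.** 22 practices, cohorts of 9, practice ICC 0.03, REML fit with a practice random effect only. There were 2,000 replicates for 5 cohorts per practice and 1,000 for 8. Rejection rates:

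| Pattern of mode | ρ = 0 | ρ = 0.03 | ρ = 0.05 | ρ = 0.10 |
|---|---|---|---|---|
| Random by cohort, 5 cohorts | 5.8% | 8.0% | 10.7% | 14.8% |
| Random by cohort, 8 cohorts | 4.4% | 8.7% | 10.9% | 13.9% |
| One switch per practice, 5 cohorts | 5.5% | 8.4% | 10.1% | 13.8% |
| One switch per practice, 8 cohorts | 5.5% | 6.5% | 9.6% | 16.7% |
| Constant within practice, 5 cohorts | 5.3% | 5.2% | 5.0% | 4.9% |
| Constant within practice, 8 cohorts | 5.1% | 5.2% | 5.6% | 3.9% |

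With the outcome cut into a 1-to-6 session count (random by cohort, 5 cohorts), rejection was 8.0% and 13.0% at a latent cohort ICC of 0.05 and 0.10.

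**4. With cohort within practice added** (random by cohort, 5 cohorts, 600 replicates, Monte Carlo standard error about 0.9 percentage points): 5.7%, 5.0% and 5.7% at ρ = 0, 0.05 and 0.10. That is about nominal.

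**The case against.** The strongest reply has four parts.

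- **The plan already knows that groups matter.** It will examine between-group variability by arm, use diagnostics to compare model specifications, and run sensitivity analyses on delivery mode. This is true, so it would be wrong to infer that the plan overlooks cohort clustering. But none of these steps puts a group effect into the hypothesis III interaction test. Even if the group provision were read as covering every hypothesis, retention would depend on an undefined amount of variability.
- **The inflation is conditional.** Mode is described as mainly a practice decision. Where each practice keeps one mode, the practice effect suffices and the test holds its level. This stands. The staggered return to in-person visits, with new cohorts planned about every three months, makes switching plausible, but the documents do not say how common it is.
- **The tests are exploratory.** This stands and limits the importance of the point. Reporting every subgroup test and weighing their number does not repair a standard error that is too small.
- **Language is less clear than mode.** A reader might infer that arm by cohort language is also planned on attendance. The documents do not say so. Language appears only in the general moderator list. The hypothesis III paragraph names mental illness alone, and the detailed moderator model covers hypotheses I, II and IV. The same argument would apply if language were tested on attendance.

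**Conclusion.** The point holds in a limited form. As written, the arm-by-mode test on sessions attended is anti-conservative when mode varies between cohorts within a practice and attendance is correlated within cohorts. At a cohort ICC of 0.03 to 0.05 the type I error is about 8% to 11% against 5%. One simulated pattern was lower, at 6.5%. That ICC range is borrowed from the plan's practice-level values. The error would be larger if groups vary more than practices, which the plan itself allows.

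Two stronger readings are not supported. One is that the error is around 15% or more: that needs a cohort ICC of about 0.10 or higher, above any ICC in the plan. The other is that the main comparison of arms on attendance fails for the same reason. It does not, because arm is constant within a practice and the practice effect carries that contrast.

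**What to change.** 1. For sessions attended, among patients assigned to a cohort, extend the group-within-practice random effect to the hypothesis III model and keep the practice effect.
2. Keep the group effect whenever a cohort-level moderator is in the model (mode, and language if it is tested on attendance). Do not make it subject to the sufficient-variability rule.
3. Test the interaction with between-cohort degrees of freedom: Kenward-Roger for a linear model, and containment, between-within or a cohort-level method for a Poisson or ordinal model, where Kenward-Roger is not automatically available.
4. In the heterogeneity section, identify mode and language as cohort-level moderators, separate from the patient-level ones, and say whether language is to be tested on attendance.

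Acceptance of services is outside this change, because patients who decline may have no cohort.

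The cost is a few sentences in the analysis plan, one more random effect, and a cohort identifier in the analysis file. Attendance is already recorded session by session. Intervals for these exploratory interactions would widen by about √1.24 = 1.11 to √1.40 = 1.18 times at the assumed cohort ICCs.

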C.4.1 Study Design. This is a pragmatic, cluster randomized comparative effectiveness trial. Given the complexity of systems and processes needed to implement SMAs, and the possibility of contamination effects, randomization will be clustered at the practice level using covariate constrained randomization.⁵⁵⁻⁵⁷ Twenty-two practices will be randomly assigned to either standardized or patient-driven diabetes SMAs (10 per condition). During the 24-month implementation period, each practice will conduct SMAs with around 8 cohorts of 8 to 10 patients each (ultimately yielding up to 72 patients per practice). The initial plan is that cohorts of adult patients with T2DM will progress through 6 weekly SMA sessions, and a new cohort will begin every 3 months, but practices can choose their own timeline. A mixed-methods evaluation will include quantitative (practice and patient-level surveys, electronic health records (EHR), and participation and intervention fidelity tracking data) and qualitative (practice and patient interviews, observation) components.

Sample Size and Power Calculations: Previous power calculations used 1,440 total patients, which is not feasible given recruitment challenges by practices. We are expecting N (total) = 22 clinics, 1,000 patients (11 clinics and 500 patients

PRINCIPAL INVESTIGATOR (LAST, FIRST, MIDDLE): [name]

per condition), allowing for ~15-20% attrition (leaving 400 patients per arm). However, we are estimating power based on 20 practices and provide a possible range of potential power to detect main effects. We estimated the minimum effect sizes detectable for different power calculations for various numbers of practices and patient sample sizes and intraclass correlations (ICC; see table below), with effect sizes of approximately .29 to .35 for intent-to-treat analyses of primary outcomes with a type-1 error rate of .05. Power for planned subgroup analyses for patient characteristics (e.g., mental illness, health literacy) is also shown. An effective sample size of 67 per group is required to detect a medium linear trend effect between groups (increasing from 0 to .5SD) using general linear mixed models with random slopes and intercepts.⁵⁸

| Practices per arm: N | Patients per practice: N | With 15-20% attrition: N | ICC | Effective sample size | Detectable difference (effect size) | Power |

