We will use **quantitative and qualitative methods** to evaluate research questions and test hypotheses for patient and practice-level outcomes. Table 4 summarizes outcomes, measures, data sources, and timing and administration.

Patient-level outcomes measures:

Patient-reported outcomes (PC-3). Patient stakeholders selected diabetes distress as the primary patient-centered outcome (RQ-6). Diabetes distress will be measured using the 17-item Diabetes Distress Scale (DDS-17), a validated self-report survey.^{60,61} Respondents indicate on a scale from 1 to 6 the extent to which they experience bothersome distress in four domains: emotional, regimen, interpersonal, and healthcare navigation burden. The DDS-17 has been demonstrated to be strongly related to and prospectively predictive of diabetes self-management behaviors as well as glycemic control, and has discriminant validity for depression measures.¹⁴ Additional patient-reported outcomes measures to be administered were selected by patients and/or reflect SDT constructs from the conceptual model; all are established valid and reliable self-report measures (IR-4). Perceived autonomy support in health care settings and self-efficacy (SDT constructs) will be measured using the 6-item Health Care Climate Questionnaire (HCCQ) and the 4 item Perceived Competence for Diabetes Scale (PCDS).⁷³ Diabetes self-management behaviors will be measured using the Summary of Diabetes Self-Care Activities (SDSCA). The 11-item SDSCA assesses self-reported dietary adherence, physical activity, and medication adherence, and is the most widely used and validated brief patient report scale for diabetes self-management behaviors.⁷⁴ Patient out of pocket cost and time commitments will be collected using questions drawn from existing surveys. Out of pocket cost measures will use questions drawn from the Medical Expenditure Panel Survey and the National Health Interview Survey.⁷⁵ Measures of the amount of time patients spend receiving, waiting for, and traveling to receive medical services will be drawn from the American Time Use Survey.⁷⁶ Health literacy, a potential moderator, will be measured using the validated 3-item Health Literacy Scale.

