For hypotheses I, II and IV, moderator analyses involve inclusion of main effect for time, arm, moderator variable, time x arm, time x moderator, arm x moderator, and time x arm x moderator ***interaction term*** in the model (HT-3). The three-way interaction term tests for differential intervention effectiveness in subgroups identified by the moderator variable. Due to the exploratory nature of these analyses, we do not plan to adjust for multiple comparisons in moderator analyses using the subgroups defined above. However, interpretation of results will include reporting on all subgroup analyses and take into account the number of subgroup analyses performed (HT-4).

Patient cost/time and practice resource/time data analysis. The following analyses will be conducted by [name]. Patient cost/time and practice resource and staff time use data will be examined using simple descriptive measures, including minimum and maximum values (range) and means. Descriptive measures will be calculated for practices in each arm of the study as well as for each type of practice and by level of patient participation. To examine the extent to

PRINCIPAL INVESTIGATOR (LAST, FIRST, MIDDLE): [name]

which practice resources are related to patient participation in SMAs, we will examine multiple values calculated for each measure, including a practice-level value, per-patient that agrees to complete these measures, and the value of the measure per-patient that completes different numbers of sessions. Outlier values of these measures will be confirmed with practices prior to the final analysis of these measures. Results from the analysis of practice resources and staff time use will not involve formal statistical tests of differences, as these data will be used for descriptive rather than comparative purposes.

C4.4.2d.2 Qualitative Analysis

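### The exploratory health-literacy moderator test is described only as high versus low, with no cut-point, although a scale score is collected; if the effect varies steadily with literacy, a split keeps about 54% to 64% of the effective sample

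*Combined protocol and SAP*

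**What the plan says.** - **Measurement.** Section C.4.4.2c: "Health literacy, a potential moderator, will be measured using the validated 3-item Health Literacy Scale". Table 4 places this survey at the 1st session.
- **Contrast.** The heterogeneity paragraph of C4.4.2d.1 lists the moderator comparisons, among them "male vs. female, Hispanic ethnicity vs not, high vs. low health literacy". No section gives a scoring rule, a cut-point or a reason for one.
- **Test.** The next paragraph sets out the time, arm and moderator terms and their interactions for hypotheses I, II and IV: "The three-way interaction term tests for differential intervention effectiveness in subgroups identified by the moderator variable". These analyses are called exploratory and carry no multiplicity adjustment.
- **Power.** Section C.4.1: "Power for planned subgroup analyses for patient characteristics (e.g., mental illness, health literacy) is also shown".
- **Form left open elsewhere.** The list of covariates and potential moderators in C4.4.2d.1 includes "insulin dependence, baseline diabetes distress, health literacy, and mental illness", with no statement of how any of them is coded.

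**The concern.** Sex and ethnicity enter the moderator list as categories. Health literacy does not: it arrives as a score and, on the natural reading, is cut in two before the interaction is tested. Cutting a score discards the differences between patients within each half, and interaction tests have little information to spare. The plan itself concedes that the sample may detect only large effect modification.

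Two things are at stake. A real gradient in benefit across literacy is more likely to be missed. And because no cut-point is fixed, the answer can depend on where the cut is placed once the data are in hand. Literacy is not a marginal characteristic here: section B says that the trial is meant to show for whom the patient-driven model works, and the stakeholder account in the same section ties tailoring to health literacy.

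**Working it through.** **Inputs from the documents (C.4.1 and its table)**
- Patients with follow-up: the text has "allowing for ~15-20% attrition (leaving 400 patients per arm"; the table uses 385 or 445 per arm. I use 385.
- Subgroup rows: 96 per arm, 9.6 per practice; detectable effect .46 at ICC 3% and .49 at ICC 5%.
- Alpha .05 in C.4.1; C4.4.2d.1 adds "Hypothesis tests will be two-sided".

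**Step 1. Reproduce the plan's table.** Effective n = n / (1 + (m − 1) × ICC); detectable effect = (1.96 + 0.84) × √(2 / effective n).
- Main rows: effective n 193.1, 140.2, 181.2, 133.9; effects .285, .335, .294, .342. Stated: 193, 140, 181, 134 and .29, .34, .30, .35.
- Subgroup rows: 96 / (1 + 8.6 × .03) = 76.3 and 96 / (1 + 8.6 × .05) = 67.1; effects .454 and .484. Stated: 76, 67 and .46, .49.

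The table reproduces, with effects rounded up. Its subgroup rows are the arm difference detectable inside a subgroup. They do not give power for an interaction, and no such figure appears in the documents.

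**Step 2. Information kept by a split.** For a normal score with a linear interaction, splitting at share p multiplies the test's signal by r = φ(z_p) / √(p(1 − p)). The effective sample kept is r².

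| Split | r | r² |
|---|---|---|
| 50/50 | 0.798 | 64% |
| 30/70 | 0.759 | 58% |
| 25/75 | 0.734 | 54% |

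The 25/75 split is the nearest to anything in the documents (96/385 = 25%; 96/445 = 22%), but that subgroup size is generic and not specific to literacy.

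**Step 3. Power.** Let d be the assumed difference in arm effect between the low and high groups, in SD of the analysed change.
- Split: SE = √(2/n_low + 2/n_high), with group sizes per arm.
- Full score: the two group means lie φ(z_p) / (p(1 − p)) apart in SD of the score (1.596 at 50/50, 1.695 at 25/75). The slope is d divided by that gap, with SE √(2/385) = .072.

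Worked case, d = .46 and 25/75:
- Split: SE = √(2/96 + 2/289) = .167, z = 2.76, power 79%.
- Full score: slope .46/1.695 = .271, z = 3.77, power 96%.
- With both sample sizes deflated by 76/96 for clustering: 69% against 92%.

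| d | 50/50: full, split, loss | 25/75: full, split, loss |
|---|---|---|
| .15 | 26%, 18%, 8 | 23%, 15%, 9 |
| .30 | 74%, 55%, 19 | 69%, 44%, 25 |
| .46 | 98%, 89%, 9 | 96%, 79%, 18 |
| .60 | >99%, 99%, 1 | >99%, 95%, 5 |

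Losses are in percentage points, from unrounded powers. At 80% full-score power the 25/75 loss is 26 points: z = 2.80 becomes 2.80 × .734 = 2.06, power 54%.

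**Step 4. Sensitivity.**
- A simulated 3-item sum with five response levels (format assumed), at 80% full-score power, loses about 12 to 25 points for most cuts near the middle of the distribution and 30 or more for extreme cuts.
- If the truth is a step exactly at the cut, the ranking reverses: split 84% against full score 63% for a symmetric score, and 85% against 72% for one piled up at the ceiling.

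All of this assumes unit SD of the analysed change and no between-practice variation in the interaction.

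**The case against.** The strongest reply is that nothing commits the analysts to a split. The high/low phrase sits in a parenthesis illustrating a general hypothesis. The model is written for a generic moderator, which could be a score, and the covariate list places literacy beside age and the comorbidity index without a form. This stands in part: a reader might infer that the plan rules out a full-score test, and it does not. But the only contrast described is two-category, and the test and power text speak of subgroups. If the form is open, it still needs fixing.

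A second reply is that no particular power loss belongs to this plan. That stands. The literacy distribution, the cut and the interaction size are all absent. A reader might take .46 as the plan's interaction effect, but it is a within-subgroup arm difference, and it exceeds the 0.30 hypothesised for the whole treatment comparison.

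Third, linearity is itself an assumption, and a validated scale may have an established cut that these documents do not show. That also stands, and is why a split should be kept in support.

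Finally, the analysis is exploratory, and mental illness is the primary target for heterogeneity. That limits the importance of the point without removing it.

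**Conclusion.** The point holds as a low-cost improvement to an exploratory analysis. A score is collected, the only moderator contrast described is high versus low, and no cut-point is given. If the arm effect changes steadily with literacy, a split keeps about 54% (25/75) to 64% (50/50) of the effective sample for the interaction. In power terms this is roughly 8 to 26 points at moderate effects and 5 or fewer at d = .60. That range rests on an assumed split between 50/50 and 25/75, an assumed effect size, a normal score and a linear effect. It is not a bound: a 20/80 split loses 30 points from 80% power.

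Two stronger conclusions might be inferred and are not supported. One is that the full score is always the better test; under a true step at the cut it is the weaker one. The other is that the trial's main result is affected; the primary comparison does not use this moderator contrast.

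**What to change.** In the heterogeneity and moderator paragraphs of C4.4.2d.1:
- State how the 3-item scale is scored.
- Make the exploratory health-literacy moderator test use the full score: time × arm × score for hypotheses I and II, and arm × score for number of sessions attended, among attendees.
- Report the estimated arm effect at a low and a high score, with confidence intervals.
- Keep one high/low split, with its cut-point fixed before analysis, as a supporting display and threshold check.
- Leave the naturally binary moderators as they are.

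Do not extend the score test to hypothesis IV or to acceptance of services. The hypothesis IV outcomes come from the clinical team (Table 4), who have no patient literacy score. Acceptance is attendance at the initial session among all invited, while literacy is surveyed at that session, so those who decline would generally have no score.

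The cost is a few sentences and one extra model per applicable outcome, with no new data. The price is the linearity assumption: the full-score test is weaker if the effect is a pure step, which the retained split is there to show.
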